2.3 Additional Analyses

During the conduct of the study, a range of actual tube weight differences of 1 g to 5.1 g was observed in contrast to a planned weight of administered gel of 2 g. In order to investigate a possible bias on the study results it was decided to add analyses (Table 2): These will be performed for the primary PK endpoints (AUC_{0-τ, ss} and C_{max, ss}) normalized by the weight of the administered gel on Day 7. Only the weight of Day 7 is used because steady state can be assumed. The analysis will also be done for the extreme value rectified PK parameters.

Please note that normalization by the actual administered dose is not intended. The diclofenac content is different in the investigated products (Diclofenac 2% versus 2.32% topical gel) and the ratio of administered doses can only be maintained by normalizing by the weight of the administered gel.

The final SAP Section 6.3.12.2 “Sensitivity Analysis” will be amended by an extra sensitivity analysis of the main analysis. There will be no changes to the structure/format of the tables, figures and listings based on this change.

Same statistical model and SAS code as per relative bioavailability will be used for additional analyses.

2.4 Supportive and Secondary Analyses

The analysis of the primary PK parameters, with and without extreme value and normalized by weight of administered gel, will also be added to the statistical analyses shown in Table 2. Primary PK endpoints in plasma will be calculated for diclofenac and capsaicin, however, the secondary analysis is not applicable for capsaicin. The statistical analyses will be added to the shells indicated in the following Table 2.

 International
 Statistical Analysis Plan Addendum

Table 2: Overview of analyses of PK parameters on Day 7

PK Parameters	Main Analysis Fixed Effects	Sensitivity Analysis Random Effect	Supportive Analysis Race	Secondary Analysis Main Without Extreme Value
Final SAP				
AUC _{0-τ,ss}	x	x	x	x
SAP Addendum				
C _{max, ss}	x	x	x	x
AUC _{0-τ, ss, norm by gel}	x	x	x	x
C _{max, ss, norm by gel}	x	x	x	x
Used shells	T 15.5:1 T 16.1.9.3:1	T 16.1.9.3:2	T 15.5:2 T 16.1.9.3:3	T 15.5:3 T 16.1.9.3:4

Norm by gel: normalized by the weight of administered gel; τ: dosing interval 0-12 hours; ss: steady state; x: requested analysis.

The first two rows in Table 2 display the planned statistical analyses described in the SAP final version 1.0. The clarified PK parameter C_{max, ss} and the additional PK parameters normalized by weight of the administered gel will be added to the statistical analyses as requested above.

 International
 Statistical Analysis Plan Addendum

3. TABLES/FIGURES

Table 3: Tables and listings referred in the text

Type	Title number	Title	Population
L	16.2.3:1	Protocol Deviations	Safety Population
L	16.2.5:1	Exposure to Study Drug	Safety Population
L	16.2.6:1	Pharmacokinetic Parameters of Diclofenac	Safety Population
L	16.2.6:2	Pharmacokinetic Parameters of Capsaicin	Safety Population
L	16.2.7:1	Adverse Events	Safety Population
T	15.1.5:1	Extent of Exposure	Safety Population
T	15.5:1	Statistical Analysis of Primary Pharmacokinetic Endpoints in Plasma by Analyte	Pharmacokinetic Population
T	15.5:2	Supportive Analysis of Primary Pharmacokinetic Endpoints in Plasma by Analyte and Race	Pharmacokinetic Population
T	15.5:3	Secondary Analysis of Primary Pharmacokinetic Endpoints in Plasma by Analyte	Pharmacokinetic Population
T	15.5:4	Not applicable output for sensitivity analysis (random effect) can be found in Table 15.5:1 and Table 16.1.9.3:2	
T	15.6.3:1	Summary of Pharmacokinetic Parameters by Product and Analyte	Pharmacokinetic Population
T	15.6.3:2	Summary of Pharmacokinetic Parameters by Product and Analyte and Race	Pharmacokinetic Population
T	16.1.9.3:1	Statistical Analysis of Primary Pharmacokinetic Endpoints in Plasma by Analyte	Pharmacokinetic Population
T	16.1.9.3:2	Sensitivity Analysis of Primary Pharmacokinetic Endpoints in Plasma by Analyte	Pharmacokinetic Population
T	16.1.9.3:3	Supportive Analysis of Primary Pharmacokinetic Endpoints in Plasma by Analyte and Race	Pharmacokinetic Population
T	16.1.9.3:4	Secondary Analysis of Primary Pharmacokinetic Endpoints in Plasma by Analyte	Pharmacokinetic Population

L: Listing; T: Table

[REDACTED]	[REDACTED]
%AUC _{ex}	Percentage of AUC _(0-inf) obtained by extrapolation
%PTF	Percentage Peak trough fluctuation

STATISTICAL ANALYSIS PLAN

The Statistical Analysis Plan (SAP) details the statistical methodology to be used in analyzing study data and outlines the statistical programming specifications for the Tables, Listings and Figures (TLFs). It describes the variables and populations, anticipated data transformations and manipulations and other details of the analyses not provided in the Clinical Study Protocol (CSP).

The analyses described are based on the final CSP, dated, 17/Oct/2016, and revised CSP, dated, 13/Feb/2017 as well as the final Data Management Plan dated 05/Jul/2017. The SAP will be finalized prior to database lock and describes the statistical analysis as it is foreseen when the study is being planned. If circumstances should arise during the study rendering this analysis inappropriate, or if improved methods of analysis should arise, updates to the analyses may be made. Any deviations from the SAP after database lock, reasons for such deviations and all alternative or additional statistical analyses that may be performed, will be described in a SAP Addendum.

1. STUDY OBJECTIVES

1.1 Primary Objective

The main objective of this study is to assess the relative systemic bioavailability of diclofenac in the presence and absence of capsaicin by comparing the systemic bioavailability of diclofenac from a combination product (Diclofenac 2% + Capsaicin 0.075% Topical Gel) with two diclofenac only products, Diclofenac Mono Gel 2% and Voltarol® 12 Hour Emulgel 2.32% Gel, following topical administration.

1.2 Secondary Objective

[REDACTED]

[REDACTED]

In order to examine potential racial differences in pharmacokinetics (PK), the study population will be stratified 50:50, Caucasian versus Black people. [REDACTED]

[REDACTED]

[REDACTED]

[REDACTED] International
Statistical Analysis Plan

2. STUDY DESIGN

This will be a multiple-dose, open-label, randomized, 3-period, 3-treatment, 6 sequence (3x3x6) crossover study with topically administered diclofenac 2% (2 g) in the presence and absence of capsaicin 0.075%, in at least 42 healthy male and female subjects (stratified 50:50 Caucasian versus Black people) in a single study center.

Details on the medicinal products can be found in Section 8.2 in the CSP. For details relevant for the statistical evaluation please refer to Section 6.3.12 of this SAP.

The study will comprise:

- Screening period of maximum 21 days.
- Three-treatment periods (each of which will include a multiple-dose period of 7 days [twice daily and only in the morning on Day 7] and two PK profile periods of 12 hours [Day 1] and 24 hours [Day 7]) separated by a wash out period of at least 7 calendar days between the last administration of the Investigational medical product (IMP) in a treatment period and the first administration of IMP in the next treatment period. Clinic stay/visits will be as follows:
 - Subjects will be admitted to the study center on Day -1 and leave the center after the morning dose on Day 2, at least 24 hours after the initial dosing on Day 1
 - Subjects will visit the study center on Days 3 and 4 for the morning dose
 - On Day 5, they will visit the center for PK blood sampling prior to morning and evening dose and will be re-admitted to the study center on the evening of Day 5
 - Subjects will leave the center at least 24 hours after the morning dose on Day 7
- A follow-up visit will occur within 72 hours after completion of the last treatment period of the study.

Before the first administration of IMPs subjects will be randomized to one of 6 treatment sequences stratified by race (Black, Caucasian), i.e., 4 Black and 4 Caucasian subjects will be assigned to each treatment sequence.

3. STUDY POPULATION

Up to 48 eligible subjects (stratified 50:50 Caucasian and Black people) will be enrolled into the study to complete the study with at least 42 evaluable subjects with respect to the planned precision of the estimated relative bioavailabilities.

In order to examine potential racial differences in pharmacokinetics (PK), subjects will be randomized to one of 6 treatment sequences stratified by race (Black, Caucasian), i.e., 4 Black and 4 Caucasian subjects will be assigned to each treatment sequence.

Detailed lists of inclusion and exclusion criteria are shown in Sections 7.3.1 and 7.3.2 of the CSP.

4. STATISTICAL BASIS FOR SAMPLE SIZE

The sample size determination is not based on a power calculation, but to assure a precise estimation of relative bioavailability ratios with respect to $AUC_{(0-\tau,ss)}$ and $C_{max,ss}$. Precision is defined as the ratio of upper to lower confidence interval (CI) limit and can also be shown in terms of the width of CIs (note that the precision is independent of the actual ratio of geometric means [gMeans] but CIs are not as can be seen in the table below).

Different estimates of the geometric coefficient of variation (gCV) for AUC and C_{max} values of topical diclofenac were found in literature (see CSP) regarding $AUC_{(0-\tau,ss)}$ and $C_{max,ss}$ of PENNSAID topical solution and regarding C_{max} and AUC_{0-24} of Voltaren topical gel. There, variability was very high, gCVs were calculated from CIs of ratios which ranged from 21 to 41 % and even 57% in one case. Based on this data, a gCV of 40% was used for estimation of precision for different scenarios.

Assuming an intra-individual variability of 40% for both $AUC_{(0-\tau,ss)}$ and $C_{max,ss}$, the trial will need N=42 analyzable subjects in order to achieve two-sided 90% CIs meeting a precision of 1.42 with a probability of 95%.

[REDACTED] International
Statistical Analysis Plan

Table 1 Expected Two-sided 90% Confidence Intervals for Different Ratios T/R and gCVs for a Sample Size of 42, Coverage Probability = 95%

gCV [%]	T/R ¹	90% CI	Precision upper CL/lower CL
40	0.95	80 - 113	1.41
	1.00	84 - 119	1.42
	1.05	88 - 125	1.42
45	0.95	78 - 115	1.47
	1.00	83 - 121	1.46
	1.05	87 - 127	1.46

1: T/R: T=Test IMP, R=Reference IMP

5. RANDOMIZATION

A randomization schedule was provided by [REDACTED] Biostatistics. The randomization schedule was generated utilizing the PROC PLAN procedure of SAS® software.

Forty-eight subjects will be randomized to a 6 sequence Williams square design for 3 periods and 3 treatments: ABC, BCA, CAB, CBA, ACB, BAC. Subjects will be randomized to 1 of 6 treatment sequences balanced over race. Thus, of each race, 4 subjects will be allocated to a particular sequence.

Subjects will be assigned randomization numbers [REDACTED].

6. STATISTICAL ANALYSIS CONVENTIONS

6.1 Analysis Variables

6.1.1 Demographic and Background Variables

The following demographic and anthropometric information will be recorded:

- Date of informed consent
- Medical history (including previous and current medical conditions and medications)
- Alcohol and smoking history
- Age
- Gender

[REDACTED] International
Statistical Analysis Plan

- Race
- Height, without shoes (cm)
- Body weight (kg)
- Body mass index (BMI) calculated as $[\text{weight}/\text{height}^2]$ (kg/m²)

All medical history will be coded using Version 20.0 of the Medical Dictionary for Regulatory Activities (MedDRA).

6.1.2 Safety Variables

6.1.2.1 Adverse Events

An adverse event (AE) is defined as any untoward medical occurrence in a clinical investigation subject administered a pharmaceutical product and which does not necessarily have a causal relationship with this treatment. An AE can therefore be any unfavorable and unintended sign (including an abnormal laboratory finding, for example), symptom, or disease temporally associated with the use of a medicinal product, whether or not considered related to the medicinal product. More details regarding serious adverse events (SAEs), AEs of special interest, classification of AEs and causal relationship of AEs are defined in the CSP section 12.

All AEs will be coded using version 20.0 of the Medical Dictionary for Regulatory Activities (MedDRA).

A treatment-emergent adverse event (TEAE) is defined as an AE that begins or that worsens in severity after at least one dose of the study drug has been administered.

Any AEs with incomplete start and end dates/times will be treated as follows:

- Adverse events with unknown start and/or end times (but where the date is known) will be imputed with a time of 00:00 h for the tabulations but will be shown as NK:NK in the listings (where NK = Not Known).
- Adverse events with completely unknown start dates will be considered as treatment-emergent for the tabulations and will be shown as NK in the listings.

[REDACTED] International
Statistical Analysis Plan

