7.1. Overall Study Design and Plan: Description

7.1.1. Study Design

This will be a multiple-dose, open-label, randomized, 3-period, 3-treatment, 6 sequence (3x3x6) crossover study with topically administered diclofenac 2% (2 g) in the presence and absence of capsaicin 0.075%, in at least 42 healthy male and female subjects (stratified 50:50 Caucasian versus Black people) in a single study center.

The study will comprise:

- Screening period of maximum 21 days.
- Three-treatment periods (each of which will include a multiple-dose period of 7 days [twice daily and only in the morning on Day 7] and two PK profile periods of 12 hours [Day 1] and 24 hours [Day 7]) separated by a wash out period of at least 7 calendar days between the last administration of the IMP in a treatment period and the first administration of IMP in the next treatment period. Clinic stay/visits will be as follows:
 - Subjects will be admitted to the study center on Day -1 and leave the center after the morning dose on Day 2, at least 24 hours after the initial dosing on Day 1
 - Subjects will visit the study center on Days 3 and 4 for the morning dose
 - On Day 5, they will visit the center for PK blood sampling prior to morning and evening dose and will be re-admitted to the study center on the evening of Day 5
 - Subjects will leave the center at least 24 hours after the morning dose on Day 7
- A follow-up visit will occur within 72 hours after completion of the last treatment period of the study.

Before the first administration of IMPs subjects will be randomized to one of 6 treatment sequences stratified by race (Black, Caucasian), i.e., 4 Black and 4 Caucasian subjects will be assigned to each treatment sequence.

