 11. Tests for human immunodeficiency virus (HIV), Hepatitis B and Hepatitis C, performed using commercially available test kits. Pre- and post-test counseling will be provided as appropriate.
 12. Urinalysis (dipstick): Glucose, bilirubin, ketone, specific gravity, blood, pH, protein, urobilinogen, nitrite and leucocytes. Abnormal urinalysis results may be repeated at the discretion of the Investigator. All results will be reported.
 13. Serum pregnancy test (quantitative β -HCG [beta human chorionic gonadotropin] method) at screening. On admission to each treatment period (Day -1 each period) urine pregnancy testing will be performed. If any of these tests are positive, subjects will not be allowed further participation in the study. Urine pregnancy test at the follow-up visit.
 14. Using a rapid, one-step screening test for simultaneous, qualitative detection of multiple drugs and drug metabolites, such as amphetamines, barbiturates, benzodiazepines, cocaine, opiates, phencyclidine (phenylcyclohexylpiperidine), tetrahydrocannabinol, methadone, methamphetamine, tricyclic antidepressants, oxycodone and propoxyphene. Subjects with alleged false positive test results will be excluded from the study. However, a positive test may be repeated once at the discretion of the Investigator.
 15. Cotinine testing using commercially available testing procedures.
 16. Alcohol breath test using a portable breath alcohol measuring device. The test will be performed at screening, on admission to each treatment period and at random. If any of these tests are positive, subjects will not be allowed further participation in the study.
 17. The tubes will be weighed before and after dosing, whenever the subject is at the study center.
- [REDACTED]
19. IMP will be self-administered in the morning and evening (12 hours apart) on Days 1 to 6 and only in the morning on Day 7. Refer to [Section 7.2.6](#) for window allowance.
 20. Blood for PK analysis will be collected on Day 1 at the following time points: 0 hours (prior to morning dose) and at 0.5, 1, 2, 3, 4, 6, 8, 10 and 12 hours post-dose (prior to evening dose) (total: 10 samples per treatment period) and on Day 7 pre-dose at 0 hours and at 0.5, 1, 2, 3, 4, 6, 8, 10, 12, 14, 16, 18, 20 and 24 hours post-dose (15 samples per treatment period). PK sampling should take preference over other assessments.

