12. ADVERSE EVENTS

Each subject will be carefully monitored by the Investigator for AEs. In addition, information on AEs will be obtained from the subjects by study staff regularly questioning them, although no leading questions will be asked. When an AE occurs, the PI will decide whether to withdraw the subject from the study and/or initiate appropriate treatment. After withdrawal from the study, it will be ensured that the subject is given appropriate medical care, if needed, which may take the form of referral to a physician.

In the case of any event requiring medical intervention occurring during the clinic stay, the Investigator will institute general supportive measures including, where necessary, respiratory assistance and cardiopulmonary resuscitation.

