12.5. Allocation of Adverse Events to Treatment Groups

AEs are allocated to treatment groups based on start date/time of the AE in relation to dosing in each period.

- All AEs with start date/time prior to dosing in period 1 are pre-treatment AEs and are assigned to screening.
- All AEs with start date/time after the date/time of first dosing in period 1, but before dosing in period 2, would be assessed against the treatment received in period 1.
- AEs with start date/time after the date/time of first dosing in period 2, but before dosing in period 3 would be assessed against the treatment received in period 2.
- AEs with start date/time after the date/time of first dosing in period 3 would be assessed against the treatment received in period 3.

With this definition AEs occurring in wash-out are assessed against the treatment received in the preceding period. AEs up to the follow-up visit would be assessed against the treatment received in period 3 if the start date/time of the AE was after dosing in period 3.

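### Setting unknown AE start times to 00:00 removes untimed post-dose Day 1 events of period 1 from the by-product TEAE tables and leaves their product uncertain in periods 2 and 3

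*SAP*

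**What the plan says.** - **Imputation.** SAP 6.1.2.1, on incompletely timed events: "unknown start and/or end times (but where the date is known) will be imputed with a time of 00:00 h for the tabulations". The rule is the same for every study day.
- **Unknown date.** The next bullet of that section reads: "Adverse events with completely unknown start dates will be considered as treatment-emergent for the tabulations".
- **TEAE.** The same section gives this definition: "is defined as an AE that begins or that worsens in severity after at least one dose of the study drug has been administered".
- **Tabulation.** SAP 6.3.13.1 summarises TEAEs by product. It assigns an event to the treatment period in which it starts and refers in brackets to the TEAE principle. Table 15.3.1:1 in SAP 8 is a by-product TEAE summary.
- **Protocol allocation.** Protocol 12.5 works from dose to dose: "All AEs with start date/time prior to dosing in period 1 are pre-treatment AEs and are assigned to screening". For the next interval the rule is: "start date/time after the date/time of first dosing in period 1, but before dosing in period 2, would be assessed against the treatment received". The product meant is that of period 1, and later periods follow the same pattern. Wash-out events go to the preceding product.
- **Treatment period.** Protocol 2 starts a treatment period at its first study procedure, not at the first dose. Admission is on Day -1.
- **Dosing time.** Protocol Table 7-1, footnote 19: "IMP will be self-administered in the morning and evening (12 hours apart) on Days 1 to 6".

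The SAP Addendum (2.1) changes only a footnote in the AE listing.

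**The concern.** An untimed event on Day 1 of a period is set to midnight, before that morning's dose, even if it began after the dose. In period 1 this turns a treatment-emergent event into a pre-treatment one. The two bullets of SAP 6.1.2.1 also pull in opposite directions: an event with no start date at all is counted as treatment-emergent, while an event with a known Day 1 date is not. The better-documented event is the one lost.

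In periods 2 and 3 the event remains a TEAE, because earlier doses have been given, but its product can depend on which document the programmer follows. That conflict also reaches events with known times. An event between Day -1 admission and the first dose of period 2 or 3 goes to the preceding product under Protocol 12.5, but to a product not yet given under the treatment-period reading. A wash-out event goes to the preceding product under 12.5 and falls in no treatment period under the other reading.

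If untimed Day 1 events are equally common on all products, the counts are too low but no between-product bias arises. If they are commoner on one product, its excess is understated. Equal rates cannot be taken for granted: Protocol 5.1 describes warming, burning and stinging sensations with capsaicin, with desensitisation only after repeated applications. The documents give no rates.

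**Working it through.** **Step 1: follow one event through the rules.** Take an event that truly begins 2 hours after the first morning dose of a period, with its time unknown. The clock time of dosing is not given, so 06:00, 08:00 and 11:00 were assumed; the result is the same for all three.

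| Period | True status | TEAE after imputation (SAP 6.1.2.1) | Protocol 12.5 after imputation | SAP 6.3.13.1 with Protocol 2 definition |
|---|---|---|---|---|
| 1 | TEAE, period 1 product | No | Screening | Period 1, but not tabulated as a TEAE |
| 2 | TEAE, period 2 product | Yes | Period 1 product | Period 2 product |
| 3 | TEAE, period 3 product | Yes | Period 2 product | Period 3 product |

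Untimed events that truly began before the dose on Day 1 are placed correctly in period 1. In periods 2 and 3 they are placed correctly only under 12.5.

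**Step 2: count the exposure.** SAP 5 gives sequences ABC, BCA, CAB, CBA, ACB and BAC, with 4 subjects of each race per sequence, so 8 per sequence.

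- Total: 6 × 8 × 3 = 144 subject-periods, 48 per product.
- Period 1: each product comes first in two sequences, 2 × 8 = 16 per product, 48 in all.
- Periods 2 and 3: 96 subject-periods, 32 per product. Each of the six ordered pairs (preceding, current) occurs in two sequences, giving 16.

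**Step 3: expected loss in period 1 (either reading).** Let p be the rate of untimed post-dose Day 1 events per subject-period. It is not in the documents; the values below are assumptions. Expected loss = 48p, and the chance of losing at least one = 1 − (1 − p)^48.

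| p | Expected lost TEAEs | Chance of at least one |
|---|---|---|
| 0.5% | 0.24 | 21% |
| 1% | 0.48 | 38% |
| 2% | 0.96 | 62% |

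**Step 4: effect on product B minus product A.** Write pA, pB and pC for the product rates.

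- Truth: 48pB − 48pA = 48(pB − pA).
- Treatment-period reading (only period 1 lost): 32pB − 32pA = 32(pB − pA).
- Protocol 12.5 (period 1 lost, the rest moved back one product): B receives 16pA + 16pC and A receives 16pB + 16pC, so the difference is −16(pB − pA).

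With pA = pC = 0.5% assumed:

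| pB | Truth | Treatment-period reading | Protocol 12.5 |
|---|---|---|---|
| 0.5% | 0 | 0 | 0 |
| 1% | +0.24 | +0.16 | −0.08 |
| 2% | +0.72 | +0.48 | −0.24 |

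Under 12.5 the contribution of these events changes sign, but every figure in this range is below one event.

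**The case against.** **The conflict in periods 2 and 3 rests on one reading.** The SAP does not define a treatment period. Its bracketed reference to the TEAE principle, and its measurement of wash-out from last to first administration (SAP 2), suggest that 6.3.13.1 may be shorthand for Protocol 12.5. The other reading leaves wash-out events in no period, which is unlikely to be intended. This has weight, but the protocol's own definition supports the other reading, and SAP 6.3.1 takes each period's baseline from a pre-dose measurement within that period. If the dose-based reading is right, the documents agree and both charge the untimed post-dose event to the wrong, preceding product. The imputation still needs correcting.

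**The number is small and partly controlled.** The protocol says of each period: "Subjects will be admitted to the study center on Day -1 and leave the center after the morning dose on Day 2". They are thus in-house throughout Day 1, and "information on AEs will be obtained from the subjects by study staff regularly questioning them". Missing times can be queried (Protocol 10.5), application sites are inspected at scheduled times, and the listings show pre-treatment events and TEAEs with unknown times marked. Enrolment is up to 48, so period 1 exposure could be lower; with 42 subjects the expected loss would be 42p, or 0.21 to 0.84 events over the same range. All of this stands and limits the importance of the point. It does not make the rule right.

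**The remedy can misplace events too.** Something untimed that happened before dosing, for instance at cannula insertion, could be charged to a product not yet applied. That is true. It errs in the same direction as the SAP's own rule for unknown dates.

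**Conclusion.** The concern holds. For period 1 the error follows from the text under either reading: an untimed event beginning after the first dose on Day 1 is lost from the by-product TEAE tables unless it later worsens. For periods 2 and 3 the documents can give different products, depending on how SAP 6.3.13.1 is read, and need to be reconciled.

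The likely effect is below one event over the assumed rates of 0.5% to 2%, for full enrolment of 48. The AE summaries are counts, the PK endpoints are untouched, and application-site and tolerability data are reported separately. This is a rule worth correcting because it is wrong as written and cheap to mend, not because it threatens the trial's conclusions. Confidence is high for period 1; the product conflict in periods 2 and 3 is conditional on the reading.

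**What to change.** 1. On each period's first-dosing date, impute an unknown AE start time as just after that period's first dose, unless the AE is known to have begun earlier (for example, its recorded end precedes the dose). Keep 00:00 on all other days.
2. Impute an unknown end time as 23:59. Otherwise a Day 1 event with both times unknown would end before its imputed start. The present rule already does this to a same-day event with a known afternoon start and an unknown end.
3. Make SAP 6.3.13.1 refer explicitly to the dose-to-dose allocation of Protocol 12.5, so that each event has one product.

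The cost is three sentences in the SAP or its addendum and two derivation rules. The downside is that a few events that truly began before the dose on Day 1 may be counted as treatment-emergent or charged to the new period's product.
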